1. INTRODUCTION

1.1 Background and rationale

Lung cancer is one of the leading causes of death worldwide. Of the 7.3 million deaths caused by cancer every year, 17% are due to Lung Cancer. Prevalence of this disease during 2006 alone in Europe was 386,300 total cases, and 334,800 died during the same period¹.

Of the entire lung cancer population, Non-Small Cell Lung Cancer (NSCLC) is the most common (around 80%) compared with Small Cell Lung Cancer (SCLC)². Squamous Cell Lung Cancer and Adenocarcinoma are the most common subtypes in Europe between 46.5%³-33%⁴ and 23.6%³-30%⁴ respectively.

Histopathologically confirmed lung cancer is essential for optimal management of the individual patient and must be secured before chemotherapy and radiotherapy are initiated. However, in rare cases it may be impossible to obtain tumour tissue for examination due to multiple significant co-morbidities or poor performance status. Furthermore, resources available for obtaining correct diagnosis and TNM classification are likely to differ among centres, exemplified by the lack of resources for PET examination in many sites throughout Central Eastern Europe and Russia.

According to national and international guidelines, surgery, chemotherapy and radiotherapy are the cornerstones of NSCLC treatment. Individualized supportive care should constitute an essential element in the management of all patients with NSCLC. Treatment choices are determined by the stage of the disease at each moment and the patient's individual condition (performance status, co-morbidity and age).

The median survival for patients with stage IIIB or IV disease with current first-line chemotherapy regimens is approximately 7-10 months, the one-year survival rate is 35% and response rates range between 17-37%. Once patients experience treatment failure with initial therapy, response to further systemic treatment is approximately 10% Further progress is anticipated with the novel therapeutic approach of combining existing chemotherapy with drugs that target specific signalling pathways of lung cancer progression.

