3. STUDY PLAN AND PROCEDURES

3.1 Overall study design and flow chart

This is a multinational, multicentre, non-interventional, prospective cohort study to be carried out in a representative selection of hospitals in order to assess lung cancer management in countries throughout Central Eastern Europe and Russia. Within the scope of this study, no diagnostic or monitoring procedures in addition to the routine procedure will be applied to the patients.

To ensure a valid picture of real life management, sites will be selected focusing on representative hospitals where lung cancer patients are being managed, in all participating countries.

All NSCLC patients attending the responsible department of treating this type of patients (e.g. Oncology Department, Pulmonology Department) for the first time (regardless of whether the patient is diagnosed with locally, advanced or metastatic disease) at the participating sites from the first of January 2010 to the end of July 2010. Patients diagnosed, or even treated, in other departments within the same hospital or in another hospital are susceptible to be included in the study if full access to the patient's medical record is made available.

Patients could be retrospectively included in case of not receiving the Ethics Committee approval by the first of January 2010, but only those patients attending for the first time during the enrolment period.

Information regarding patient and disease characteristics will be taken from the medical record, as well as management approaches regarding the visit plan, diagnostic tests performed and therapies received by the patient.

A sample of patients will be invited to complete Quality of Life questionnaires when coming to the responsible department of treating this type of patients for assessment. PROs will be collected at each evaluation visit from the first visit (diagnosis) to last visit (after 12 months). PROs will not be completed at treatment administration visits and/or disease- or treatment-related event visits.

The data source for this study will be the medical record at the responsible department of treating this type of patients for each patient. Neither visits nor interventions will be carried out for the study purposes.

Protocol of Non-Interventional Study Drug Substance: N/A

NIS Code: NIS-ORU-IRE-2009/1

Version No: 4.0 Date: 8 December 2009

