6.2 Analysis of outcome variables in relation to objectives and hypotheses

Three groups will be created from baseline evaluation for the purpose of data analysis. The patients will be divided according to the baseline stage of their disease (non-advanced NSCLC patients, locally advanced NSCLC patients and metastatic NSCLC patients). For each of them the following variables will be considered:

- Clinical evolution from baseline to each visit:
 - o Changes in number of disease-related symptoms.
 - o Changes in the extent of the disease.
- Treatment response from baseline to each visit:
 - o Number of patients with complete response to treatment.
 - Number of patients with partial response to treatment.
 - Number of patients with stable disease under treatment.
 - o Number of patients with progression of disease after treatment.
 - O Progression-free time from the last progression or diagnosis to new progression of disease during the study period. The main analysis of the time to disease progression will be a Cox proportional hazards model to estimate the hazard ratio of progression among the analysis groups, with 95% confidence intervals. This will be a 2-sided test of the hypothesis, with a statistical significance level of 0.05. The assigned treatment will be included as a covariate.
- Treatment-related events.

Protocol of Non-Interventional Study

Drug Substance: N/A

NIS Code: NIS-ORU-IRE-2009/1

Version No: 4.0 Date: 8 December 2009

> o Mean number of patients with any treatment related event during the study period.

> o Mean number of patients with any serious treatment related event during the study period.

Mortality.

- o Number of patients with documented death during the study period.
- o Number of patients with a documented death due to NSCLC during the study period.

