6.3 Method of statistical analysis

Considering the study objectives, the analysis strategy will be as follows:

A descriptive analysis approach will be used to analyse NSCLC population, clinical management, clinical outcomes and health care resources.

Descriptive statistics will include frequency tables (n, mean, median, standard deviation, minimum and maximum for continuous variables and n, frequency and percentage for categorical values).

The assessment of different associations will be as follows:

Logistic and general linear models (GLM) will be used to assess the association of patient characteristics (including stage of disease, histology, PS, etc) and clinical management (independent variable) with clinical outcome variables (clinical evolution, treatment related events, mortality). The interest will separately focus on the treatment differences between each of them or a group of them used. Model-based point estimates of odds ratios and corresponding 95% confidence intervals will be reported (when applicable). P-values will be reported for comparisons between different treatments.

A descriptive analysis approach will be used to assess factors related with the use of health care resources, and a comparison of the level of use of health care resources will also be made.

The assessment of quality of life will be as follows:

Changes in FACT-L total score from first visit to the visit prior to a specific treatment response with focus on treatment differences. This is a variable of particular interest and will be analysed using an ANCOVA model.

Changes in FACT-L total score from first visit to each assessment will be analysed using an ANCOVA model.

Version No: 4.0 Date: 8 December 2009

Changes in EQ-5D total score from first visit to the visit prior to a specific treatment response with focus on the differences between treatments. This is a variable of particular interest and will be analysed using an ANCOVA model.

Changes in EQ-5D total score from first visit to each assessment will be analysed using an ANCOVA model.

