6.4 Determination of sample size

The most important aspect when selecting sites is their representativeness in each country. If 80% of NSCLC patients are being managed in large teaching hospitals, then 80% of the study sample should come from this type of hospital. Participating sites should include all the patients meeting inclusion/exclusion criteria during the inclusion period assumed to be 25-30 patients in a 6-months period, since there is no seasonal variability. (Estimated number of new lung cancer patients in large hospitals is 100-125/year).

Since the main objective is to obtain reliable information on how patients are being managed, it is essential to obtain valid information on all therapy lines. For this reason, and bearing in mind the high mortality of the disease, it is very important to have access to a sample large enough to finally provide a core group of patients likely to receive advanced treatment lines (including investigational products), and also to allow comparisons.

Assuming that generally in Central Eastern Europe and Russia 80-85%² of lung cancers are NSCLC, 80-90% of them are diagnosed at phase IIIb/IV (patients most likely to receive several lines of treatment) and of these 75-80% are treated (approximately 33% with investigational products). No published information is available regarding the proportion of these patients who will achieve further treatment lines, but for sample estimation we assumed that no more than 10% of newly diagnosed NSCLC patients would receive an active third line treatment.

It is estimated that approximately 4,000 patients will be included across several Central eastern European countries and Russia. This amount of patients would enable us to obtain a sample of approximately 400 IIIb/IV treated NSCLC patients throughout Europe.

For the descriptive analysis, 600 NSCLC phase IIIB-IV third line patients will allow us to estimate a proportion of 0.5 (taking into account that this is a novel study in NSCLC and the most pessimistic scenario must be considered) with a precision of 0.04, which means estimating 50% with a confidence interval from 46% to 54% (α =0.05).

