It was also considered that the analytical objectives of the study would require multivariate analysis to determine the above sample size. This analysis will consider the main risk variables as independent variables. Based on the formula provided by Freeman²⁶ (the sample size must be 10 times the number of variables plus one) in order to perform such multivariate analysis, and having as variables for comparison: treatment, cycle, phase, primary tumour location, extent of disease, prior surgery, age, sex, EGFR markers, habits, PS/ECOG and type of hospital, the total sample size of 4,000 patients is advised.

Protocol of Non-Interventional Study Drug Substance: N/A

NIS Code: NIS-ORU-IRE-2009/1

Version No: 4.0 Date: 8 December 2009

A sample of 25% of patients per country will be included in the Quality of Life descriptive sub-study. Whether a sample from each site in the study is included in the sub-study will depend on the number of sites participating in each country. The number of sites involved will be determined bearing in mind that 25% of the total population included in the study must be invited to participate in the Quality of Life sub-study.

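### Treatments are compared with p-values without regard to line of therapy or earlier anticancer treatment, so the comparisons are confounded by line

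*Protocol*

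**What the plan says.** Section 6.3 plans logistic and general linear models for the "association of patient characteristics (including stage of disease, histology, PS, etc) and clinical management (independent variable) with clinical outcome variables". It adds that "P-values will be reported for comparisons between different treatments". Quality-of-life changes, measured from the first visit, are also to be analysed with a focus on treatment differences.

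The only grouping is in Section 6.2: "The patients will be divided according to the baseline stage of their disease". The same section plans a Cox model for progression that compares these stage groups and carries treatment as a covariate. Its outcome is "Progression-free time from the last progression or diagnosis to new progression of disease during the study period".

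Section 6.4 lists the variables for the multivariate analysis: "treatment, cycle, phase, primary tumour location, extent of disease, prior surgery, age, sex, EGFR markers, habits, PS/ECOG and type of hospital". Prior surgery is there. Line of therapy, prior systemic therapy and prior radiotherapy are not.

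On who enters, Section 3.1 states: "Patients diagnosed, or even treated, in other departments within the same hospital or in another hospital are susceptible to be included", provided their records are fully accessible. Section 3.3.2.2 sets no exclusion criteria. Section 6.4 also says that "it is essential to obtain valid information on all therapy lines".

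**The concern.** Line of therapy affects both which drug a patient receives and how well the patient is likely to do. Section 1.1 makes the second point itself. It gives response rates of 17-37% with first-line regimens in stage IIIB/IV disease, and says that after failure of initial therapy "response to further systemic treatment is approximately 10" per cent. A model that compares drugs and leaves line out therefore attributes part of the effect of line to the drug.

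The time origins add to this. Change from baseline starts before any therapy in an untreated patient, but after earlier therapy in a pretreated one. The progression clock restarts at each progression, so intervals from different lines enter one model with no term to tell them apart.

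Section 3.2 says the study should compare treatments and help to identify effective ones. A p-value that partly reflects how late a drug is used cannot serve that purpose.

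**Working it through.** **The plan's own figure.** The protocol gives no power or effect size for treatment comparisons. Its one precision figure is 600 third-line patients for a proportion of 0.5 within 0.04. It reproduces: 1.96² × 0.25 / 0.04² = 600.2. It does not bear on confounding by line.

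**Does any named variable stand in for line?**
- Phase: Section 6.4 uses this word for stage (IIIb/IV).
- Cycle: not defined in the list. Section 4.1.2 records cycles under chemotherapy, and a cycle number is not a line number.
- Prior surgery: covers one kind of earlier treatment only.
- Stage: recorded at the first visit only (Section 4.1.1). A patient who relapses and moves to later therapy stays in the original group.
- PS/ECOG and extent of disease: related to line, but only partial substitutes.

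**Size, for response in stage IIIB/IV**

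Inputs from Section 1.1: first-line response r1 = 17% to 37%, with the midpoint 27% added; later-line response r2 = 10%.

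Assumptions: drugs A and B are equally active within each line. Their shares of first-line use, fA and fB, are not in the documents, so a range is shown.

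Formulas: crude response p = f × r1 + (1 − f) × r2; odds ratio = [pA/(1 − pA)] / [pB/(1 − pB)].

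Example with fA = 0.8, fB = 0.2, r1 = 0.17:
- pA = 0.8 × 0.17 + 0.2 × 0.10 = 0.156
- pB = 0.2 × 0.17 + 0.8 × 0.10 = 0.114
- odds ratio = (0.156/0.844) / (0.114/0.886) = 1.44

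| First-line share, A v B | r1 = 17% | r1 = 27% | r1 = 37% |
|---|---|---|---|
| 100% v 0% | 17.0% v 10.0%, OR 1.84 | 27.0% v 10.0%, OR 3.33 | 37.0% v 10.0%, OR 5.29 |
| 80% v 20% | 15.6% v 11.4%, OR 1.44 | 23.6% v 13.4%, OR 2.00 | 31.6% v 15.4%, OR 2.54 |
| 60% v 40% | 14.2% v 12.8%, OR 1.13 | 20.2% v 16.8%, OR 1.25 | 26.2% v 20.8%, OR 1.35 |
| equal shares | OR 1 | OR 1 | OR 1 |

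**Chance of a false positive.** This assumes 200 patients per drug and a two-sided 0.05 level, which the protocol states for the Cox model and which is assumed here for the other tests. By the usual power formula for two proportions, the chance of p < 0.05 with no true difference is:
- 80% v 20%: 23%, 75% and 97% for r1 = 17%, 27% and 37%
- 60% v 40%: 6% to 25%

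A check with 1,000 simulated logistic regressions at 80% v 20% gave 24.7%, 76.5% and 97.5% without line in the model, and 5.3%, 4.7% and 5.8% with it. Adjustment for line removes the error in this setting.

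**Other outcomes.** For progression the same mechanism is expected to work against late-used drugs, but the documents give no rates by line from which to size it. For deaths counted from inclusion, a patient must live long enough to receive a later line. That survival time is credited to late-used drugs and can reverse the direction.

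**The case against.** The strongest reply is that this belongs to the SAP. Section 6.1 promises one, and the covariate list in Section 6.3 is open-ended. Nothing says that lines will be pooled. The list in Section 6.4 serves a sample-size rule and is not the Section 6.3 model: histology appears in the latter and not in the former. This stands in part, since an SAP could add line. But the protocol itself fixes the grouping, the treatment covariate and the time origin, and line is absent from each.

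Second, the data are not lost. Section 4.1.2 collects drugs, onset and end dates and best response, and pretreated patients enter only with full record access. Line should be largely derivable. This stands, and it makes the fix cheap.

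Third, the response odds ratios do not describe the models to which the p-values are attached. Those name clinical evolution, treatment-related events and death as outcomes; Section 6.2 lists response separately, as patient counts. This also stands. The odds ratios illustrate the mechanism and are not forecasts of a planned result.

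Fourth, the progression clock already restarts at progression, and stage, PS and prior surgery adjust in part. True, but a clock that restarts at progression does not start at the beginning of a line, and the restart does not identify which line the interval belongs to.

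**Conclusion.** The concern holds as a weakness of the planned treatment comparisons. As written, they are confounded by line of therapy and by treatment before entry. For response in stage IIIB/IV the spurious odds ratio runs from 1 with an even spread of drugs over lines to 5.29 with no overlap, and is about 1.4-2.5 at an assumed 80% against 20% split. The size rests on a line mix that the documents do not give.

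Three stronger readings are tempting and not supported:
- A reader might infer that late-used drugs must always look worse. That follows for response and is expected for progression, but for mortality from inclusion it can reverse.
- A reader might take 1.84-5.29 as the likely size. That range requires complete separation of lines.
- A reader might infer that countries using more later lines would appear to have worse outcomes. Nothing in the documents establishes this, and survival to later lines could push the other way.

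This should be fixed before treatments are compared. It does not undermine the study's main objective, which is descriptive.

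**What to change.** In Sections 6.2 and 6.3, state that treatments are compared within line of therapy, or in models stratified by or adjusted for line and prior anticancer treatment. Set baseline and the time origin at the start of the line concerned, and allow for several lines from one patient, for example with patient-clustered standard errors. Do not pool patients pretreated at entry with untreated patients in first-line comparisons; keep them in the descriptive tables.

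Derive line from the drugs and dates already collected. Add to Section 4.1.2 a line number and a flag for anticancer treatment before the first attendance, so that the derivation does not depend on how fully outside treatment was transcribed. These need to be in the eCRF early, because an SAP written shortly before database lock could no longer have them collected prospectively.

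The cost is two eCRF fields, some wording, and fewer patients per comparison, hence wider intervals within line.

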All NSCLC patients attending the responsible department of treating this type of patients (e.g. Oncology Department, Pulmonology Department) for the first time (regardless of whether the patient is diagnosed with locally, advanced or metastatic disease) at the participating sites

Version No: 4.0 Date: 8 December 2009

from the first of January 2010 to the end of July 2010. Patients diagnosed, or even treated, in other departments within the same hospital or in another hospital are susceptible to be included in the study if full access to the patient's medical record is made available.

Methods

The inclusion period will last 6 months, from the 1st of February 2010 to the 1st of August 2010. All patients attending the responsible department of treating this type of patients for the first time during this period should be included in the study. Patients could be retrospectively included in case of not receiving the Ethics Committee approval by the first of January 2010, but only those patients attending for the first time during the enrolment period.

The follow-up period will last for at least one year (the follow-up period will be conducted until the end of July 2011, so the maximum follow-up period will comprise 18 months) or until the patient is deceased, lost to follow-up or changed to another hospital.

Information regarding patients and disease characteristics as well as clinical management approach (diagnostic methods, treatments and follow-up patterns) and final outcomes will be taken from the medical record at each evaluation visit. These visits will be performed according to normal clinical practice.

Functional status and Quality of Life (QoL) questionnaires will be collected directly from the patients immediately after obtaining informed consent.

All patients regardless of whether they are participating in clinical trials or not are eligible to be included in the study. This is a purely observational study, therefore participation in this study will not interfere with participation in a clinical trial.

Statistical Analysis

A descriptive analysis approach will be used to analyse NSCLC population, clinical management, clinical outcomes and use of health care resources.

Version No: 4.0 Date: 8 December 2009

TABLE OF CONTENTS

PAGE

SUMMA	RY OF THE NON-INTERVENTIONAL STUDY PROTOCOL	2
TABLE (OF CONTENTS	8
LIST OF	ABBREVIATIONS AND DEFINITION OF TERMS	11
1.	INTRODUCTION	13
1.1	Background and rationale	13

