4.3 Measurement of Outcomes Variables

4.3.1 Administration of Patient-Reported Outcomes (PRO)

The PRO questionnaires are self-administered and the patients will be asked to complete them at each evaluation visit. Evaluation visits are those in which an assessment of a procedure (once the responsible clinician of treating this type of patients has the results of such

Version No: 4.0 Date: 8 December 2009

procedure, and NOT at the time of the visit performing the procedure), or any other tumour evaluation is made by this person.

Appropriate procedures to minimise bias and enhance compliance will be followed throughout the study. The patient will complete the questionnaires independently, so that the answers reflect the patient's perceptions and views. Optimally, the questionnaires will be completed prior to patient-physician interview, before there are substantial professional encounters with transmission of information, such as disease status. Such information may influence the answers the patients provide on questionnaires. Information to the patients on how to complete the questionnaires is provided in the questionnaires.

It is recommended that, following completion of the questionnaires, the investigators perform the clinical evaluation. Before the patient leaves the clinic, the investigator, once the clinical evaluation is finished, should review the patient questionnaires to avoid any uncompleted responses.

The methods for collecting Patient Reported Outcomes (PRO) data are presented below.

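### FACT-L and EQ-5D change is analysed assessment by assessment, and symptoms, extent and response visit by visit, but visits are unscheduled, so these analyses have no common time point

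*Protocol*

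**What the plan says.** Section 6.3 gives the rule for FACT-L, "Changes in FACT-L total score from first visit to each assessment will be analysed using an ANCOVA model", and the matching one for EQ-5D, "Changes in EQ-5D total score from first visit to each assessment will be analysed using an ANCOVA model". Section 6.2 forms three groups by baseline stage and lists, for each, "Clinical evolution from baseline to each visit" (number of symptoms, extent of disease) and "Treatment response from baseline to each visit" (counts of patients by response category). None of these entries names a month, a window or elapsed time.

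The visits themselves have no schedule. The protocol summary, under Methods, states: "These visits will be performed according to normal clinical practice". Section 3.1 adds: "Neither visits nor interventions will be carried out for the study purposes". Section 3.2 also rules out extra visits. Section 4.3.1 defines the evaluation visit by an event. The definition opens "Evaluation visits are those in which an assessment of a procedure" and goes on to require that the result is already available, or that some other tumour evaluation is made. The only nominal times for the questionnaires are in Section 3.1: a first visit at diagnosis and a last visit after 12 months.

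Section 4.1.2 collects the date of every visit, and best response for each therapy.

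**The concern.** A per-assessment ANCOVA suits a trial with a fixed schedule, where the third assessment means the same month for everyone. Here the third assessment is whenever the third result came back. If one treatment or stage group is evaluated more often than another, the same assessment falls earlier in the disease for the first group and later for the second. Two groups with the same course over time would then show different mean changes. The group seen less often would also be represented by patients who had to survive longer to be assessed.

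The protocol gives reason to expect uneven spacing. Follow-up patterns are among the things the study sets out to describe (Section 2), and Section 1.1 expects management to vary by region and country. At stake is whether a difference in quality-of-life change between treatments, or in symptoms and response between stage groups, can be read as a difference in the patients' course and not in how often they were seen.

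**Working it through.** The protocol gives no figure for these analyses, so there is none to reproduce. The steps below show how far visit spacing alone can move an assessment. They are an illustration, not an estimate of bias.

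**Inputs from the protocol (Section 1.1).** Stage IIIB/IV on first-line chemotherapy: one-year survival 35%, median survival 7 to 10 months.

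**Assumptions, not in the documents.** Exponential survival; evenly spaced evaluation visits at 1, 2 or 3 months; the first visit counted as assessment one.

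**Step 1: are the survival inputs compatible?** The monthly hazard is −ln(0.35)/12 = 1.0498/12 = 0.0875. The implied median is 0.6931/0.0875 = 7.9 months, which lies inside the stated 7 to 10.

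**Step 2: timing of the fourth assessment.** It falls at 3 × interval: month 3, 6 or 9.

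**Step 3: share alive then.** From one-year survival, S(t) = 0.35^(t/12). From a median m, S(t) = 0.5^(t/m).

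| Assumed spacing | Month of 4th assessment | Alive, 35% at one year | Alive, median 7 months | Alive, median 10 months |
|---|---|---|---|---|
| 1 month | 3 | 0.35^0.25 = 77% | 74% | 81% |
| 2 months | 6 | 0.35^0.50 = 59% | 55% | 66% |
| 3 months | 9 | 0.35^0.75 = 46% | 41% | 54% |

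**Step 4: effect on a mean change.** Assume every group has the same course, a mean fall of 1 point per month. If death is unrelated to the rate of decline, mean change at the fourth assessment is −3, −6 or −9 points. Groups that do not differ therefore appear to differ by 3 to 6 points.

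**Step 5: what a common time point does and does not cure.** A simulation used individual slopes with mean −1 and SD 1, and multiplied the hazard of death by e^0.5 for each extra point per month of decline (all assumed). Among those alive at the fourth assessment, mean change was −2.58, −4.45 and −5.71 for spacing of 1, 2 and 3 months. When groups with 2- and 3-month spacing were compared at month 6 instead, the means were −4.46 and −4.45, so the difference due to spacing disappeared. The mean over all patients at month 6 was −6.00, so the gap due to survivor selection stayed at about 1.5 points.

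**The case against.** The strongest reply is that the protocol nowhere says patients are aligned by visit number. Its wording could describe change at every assessment, each placed by its date. Section 6.1 promises a comprehensive SAP before database lock, which is where windows and the time variable usually sit, and the visit dates needed for a time-based analysis are collected. Section 6.3 does not list the terms of the per-assessment ANCOVA, so time is not excluded from it. Much of this stands: absent windows alone would not be a finding. What remains is that the protocol names the assessment as the analysis point and ANCOVA as the model in a design without scheduled visits. Taken literally, that gives no common time point, and a SAP that used windows would have to depart from the wording.

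Some wider inferences are tempting but unsupported:

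- A reader might infer that symptoms, extent and response are to be tested visit by visit. Section 6.2 lists them as variables and counts within stage groups. The logistic and general linear models of Section 6.3 are not said to be run per visit.
- A reader might infer that country comparisons of quality of life are distorted. Comparing outcomes among countries is an objective (Section 2.1.2), but nothing ties it to the visit-indexed quality-of-life analyses, and Section 6.4 calls that work a descriptive sub-study in 25% of patients.
- A reader might extend the point to progression. That is analysed by a Cox model in time and is not touched by it.
- The FACT-L and EQ-5D analyses that Section 6.3 marks as of particular interest are anchored on the visit before a treatment response, not on every assessment. This point does not cover them.

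**Conclusion.** The point holds in a limited form. Followed as written, the per-assessment ANCOVA for FACT-L and EQ-5D, and the per-visit summaries of symptoms, extent and response, have no common time point. If assessments are aligned by order, visit spacing enters the contrasts between treatments or stage groups.

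The size cannot be derived from the documents. The move from month 3 to month 9, and from about 77% to 46% alive, rests on assumed spacing and exponential survival. It uses a survival figure for treated stage IIIB/IV patients, whereas the study enrols all stages. A reader might take those percentages as a measure of bias; they show only how far apart in time and survival the same assessment can fall. The point differences in steps 4 and 5 rest on an assumed slope and an assumed link between decline and death.

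A reader might also infer that time windows or a time-based model would settle the matter. They correct the timing. They do not remove survivor selection, which needs its own reporting.

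**What to change.** In Section 6.3, replace the per-assessment ANCOVA for FACT-L and EQ-5D by a repeated-measures mixed model with baseline score and actual time since first visit. Alternatively, keep ANCOVA but apply it at fixed windows such as 3, 6, 9 and 12 months. In Section 6.2, summarise symptoms, extent and response by the same time windows. The window width, and the rule when several assessments fall in one window, can be left to the SAP.

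For each window, report the number alive, dead and assessed, and state the quality-of-life results as conditional on being alive and assessed. If the mixed model is chosen, show the observed window means in those assessed beside it, because a model fitted to all available scores can carry trajectories past death.

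Reporting best response per therapy, already collected under Section 4.1.2, would be a useful addition but is not part of the correction.

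The cost is a change of analysis wording. Visit dates are already recorded, so no visit, procedure or data item is added. The downside is small: some assessments fall outside a window, or the model is slightly more complex.
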